6.4.7 Safety Analysis

6.4.7.1 Adverse Events

Adverse events (AEs) will be collected throughout the study and will be coded according to the current version of the MedDRA dictionary. A treatment-emergent adverse event (TEAE) is defined as an AE that started or worsened after intake of study treatment in each treatment period. If the start date is unknown then the AE will be assumed to be treatment emergent unless the partial start date, or other data (i.e. stop date) indicates differently. The TEAEs will be assigned to the treatment given prior to onset of the event. In summaries, causally related AEs will consist of AEs classified as Unlikely, Probably or Definitely related to study treatment.

Coded adverse event terms will be presented by system organ class (SOC) and preferred term and summarised by treatment group. A summary table by treatment group with total number and number of patients with adverse events, SAEs, adverse events leading to discontinuation of study treatment, causally related adverse events and severe adverse events will be produced. Further SAEs, causally related adverse events and adverse events of each intensity will be summarised by SOC and preferred term.

AEs will be presented in decreasing frequency of the total number of patients with TEAEs. All AEs, including those which are not treatment emergent, will be listed. If appropriate, SAEs and AEs leading to discontinuation of study treatment will also be separately listed.

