5 STUDY TREATMENTS

5.1 Study Treatments Administered

[figure not shown]
Patients will receive the following three single doses in a randomised sequence at Visit 2 to Visit 4:

1. 1.5 mg RPL554
2. 6 mg RPL554
3. Placebo

All three study treatments will be administered using the inhaled route with nebulised RPL554 or placebo administered using a standard Jet nebuliser (PARI LC Sprint plus a PARI TurboBOY SX compressor unit) as described in Section 5.4.2.

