8.2.3 Causality

Not Related	This category applies to those adverse events which, after careful consideration, are clearly due to extraneous causes (disease, environment, etc.)
Unlikely	In general, this category can be considered applicable to those adverse events which, after careful medical consideration at the time they are unrelated to the test drug. An adverse event may be considered unlikely to be related if or when (must have two of the following): 
1. It does not follow a reasonable temporal sequence from administration of the study treatment.2. It could readily have been produced by the patient's clinical state, environmental or toxic factors, or other modes of therapy administered to the patients.3. It does not follow a known pattern of response to the study treatment.4. It does not reappear or worsen when the study treatment is re-administered.
Possibly	This category applies to those adverse events for which, after careful medical consideration at the time they are evaluated, a connection with the study treatment administration appears unlikely but cannot be ruled out with certainty. An adverse event may be considered possibly related if or when (must have two of the following): 
1. It follows a reasonable temporal sequence from administration of the study treatment.2. It could not readily have been produced by the patient's clinical state, environmental or toxic factors, or other modes of therapy administered to the patients.3. It follows a known pattern of response to the study treatment.
Definitely	This category applies to those adverse events which the Investigator feels are incontrovertibly related to study treatment. An adverse event may be assigned an attribution of definitely related if or when (must have all of the following): 
1. It follows a reasonable temporal sequence from administration of the study treatment.2. It could not be reasonably explained by the known characteristics of the patient's clinical state, environmental, or toxic factors, or other modes of therapy administered to the patients.3. It disappears or decreases on cessation or reduction in dose and recurs with re-exposure to drug. (Note: this is not to be construed

as requiring re-exposure of the patient; however, a category of definitely related can only be used when a recurrence is observed.)

4. It follows a known pattern of response to the study treatment.

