10.4.7 Safety

Safety data including safety laboratory tests, 12-lead ECG parameters, vital signs and physical examinations, will be summarised by treatment group and time point, when appropriate. For continuous variables, the change from baseline (pre-dose at each treatment visit) to each post-dose time point will also be calculated and summarised. Data will further be illustrated by shift tables (showing changes from low/normal/high) and shift plots for selected time points.

Coded adverse event terms will be presented by system organ class (SOC) and preferred term and summarised by treatment group. A summary table by treatment group with total number and number of patients with adverse events, SAEs, adverse events leading to discontinuation of study treatment, causally related adverse events and severe adverse events will be produced. Further SAEs, causally related adverse events and adverse events of each intensity will be summarised by SOC and preferred term.

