All adverse events, whether reported spontaneously by the patient, in response to open questioning on treatment days or observed by the investigator or his/her staff, will be recorded from informed consent until the end of study visit (Visit 5). The start and stop time will be recorded and adverse events will be assessed by the investigator for the following:

- severity (mild, moderate, severe)
- chronicity (single occasion, intermittent, persistent)
- causality (not related, unlikely, possibly, definitely)
- action taken with study treatment (none, study treatment stopped, study treatment temporarily interrupted)
- other actions (none, concomitant medication, study discontinuation, hospitalisation, other)
- outcome and date of outcome (recovered or resolved, recovering or resolving, not recovered or not resolved, recovered or resolved with sequelae, fatal, unknown)
- seriousness (yes, no)

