8 DATA PRESENTATION PLAN

8.1 Tables for Section 14.1-3

Safety set used for tables if not otherwise indicated

- 14.1.1.1 Patient disposition
- 14.1.1.2 Patient flow
- 14.1.2.1 Summary of protocol deviations
- 14.1.3.1 Summary of demographic data and baseline characteristics
- 14.1.3.2 Summary of prior cystic fibrosis medications
- 14.1.3.3 Summary of life-style restrictions and nebuliser training
- 14.1.3.4 Summary of drug exposure data from nebulisations
- 14.2.1.1 Summary of plasma RPL554 concentrations [PKS]
- 14.2.1.2 Summary of pharmacokinetic parameters based on plasma RPL554 concentrations [PKS]
- 14.2.2.1 Summary of spirometry (FEV₁ and FVC) at clinic visits [FAS and CAS]
- 14.2.2.2 Summary of pharmacodynamic parameters based on FEV₁ [FAS and CAS]
- 14.2.2.3 Statistical analysis of pharmacodynamic parameters based on FEV₁ (multiplicative models) [FAS and CAS]
- 14.2.2.4 Statistical analysis of FEV₁ by assessment point (duration of action, multiplicative models) [FAS]
- 14.2.3.1 Summary of inflammatory mediators, sputum rheology and exhaled breath pH at clinic visits [FAS]
- 14.2.3.2 Statistical analysis of inflammatory mediators (multiplicative models) [FAS]
- 14.2.3.3 Statistical analysis of sputum rheology and exhaled breath pH (additive models) [FAS]
- 14.3.1.1 Summary of treatment emergent adverse events
- 14.3.1.2 Summary of adverse events by system organ class and preferred term
- 14.3.1.3 Summary of adverse events causally related to treatment by system organ class and preferred term
- 14.3.1.4 Summary of adverse events of moderate or severe intensity by system organ class and preferred term

- 14.3.1.5 Summary of adverse events with chronicity intermittent or persistent by system organ class and preferred term
- 14.3.2.1 Summary of serious adverse events by system organ class and preferred term
- 14.3.4.1 Summary of laboratory tests (continuous variables) at clinic visits
- 14.3.4.2 Summary of laboratory tests (categorical variables) at clinic visits
- 14.3.4.3 Summary of abnormal findings on laboratory data
- 14.3.5.1 Summary of vital signs at clinic visits
- 14.3.5.2 Summary of abnormal findings on vital signs
- 14.3.5.3 Summary of 12-lead ECG data at clinic visits
- 14.3.5.4 Summary of abnormal findings on 12-lead ECG
- 14.3.5.5 Summary of abnormal findings on physical examination
- 14.3.5.6 Summary rescue medication use during clinic visits
- 14.3.5.7 Summary of pregnancy tests

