8.3 Listings for Section 16.2

Safety set used for listings if not otherwise indicated

- 16.2.1.1 Randomised patients that completed the study
- 16.2.1.2 Randomised patients that were withdrawn the study
- 16.2.1.3 Visit dates by patient
- 16.2.1.4 Eligibility by patient
- 16.2.2.1 Listing of protocol deviations
- 16.2.3.1 Analysis dataset allocation by patient
- 16.2.4.1 Demographic data and baseline characteristics
- 16.2.4.2 Lung function at baseline and diagnosis of cystic fibrosis
- 16.2.4.3 Listing of medical history
- 16.2.5.1 Listing of drug exposure
- 16.2.5.2 Life-style restrictions to adhere to prior to visits and nebuliser training
- 16.2.5.3 Plasma concentrations of RPL554 [PKS]
- 16.2.5.4 Pharmacokinetic parameters [PKS]
- 16.2.6.1 Listing of spirometry data [FAS]
- 16.2.6.2 Derived pharmacodynamic parameters based on FEV₁ [FAS]
- 16.2.6.3 Listing of inflammatory mediators, sputum rheology and exhaled breath pH [FAS]
- 16.2.7.1 Listing of adverse events
- 16.2.7.2 Listing of serious adverse events
- 16.2.7.3 Listing of adverse events leading to discontinuation of study treatment
- 16.2.8.1 Listing of laboratory data
- 16.2.9.1 Listing of vital signs
- 16.2.9.2 Listing of 12-lead ECG
- 16.2.9.3 Listing of physical examination
- 16.2.9.4 Concomitant medications at entry and during the study
- 16.2.9.5 Rescue medication used during clinic visits
- 16.2.9.6 Listing of pregnancy tests (female patients)

APPENDICES

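### The SAP's definition of causally related adverse events names a level that is never recorded (Probably) and omits one that is (Possibly)

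*SAP*

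**What the plan says.** SAP 6.4.7.1 gives the only definition of the related set: "causally related AEs will consist of AEs classified as Unlikely, Probably or Definitely related to study treatment". SAP 4.5.1 lists the levels the investigator records as "causality (not related, unlikely, possibly, definitely". Protocol 8.2.3 defines the same four levels and has no *Probably*. It sets a condition for the third level, "An adverse event may be considered possibly related if or when (must have two of the following", and restricts the fourth: "a category of definitely related can only be used when a recurrence is observed".

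Protocol 10.4.7 requires a summary table by treatment group in which "causally related adverse events and severe adverse events will be produced", but does not say which levels make an event causally related. SAP 6.4.7.1 repeats that requirement. SAP 8.1 plans a table that uses the set, "14.3.1.3 Summary of adverse events causally related to treatment by system organ class and preferred term". The overview appears to be Table 14.3.1.1, although its title does not mention causality.

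**The concern.** The rule cannot be applied as written to the data that will be collected. One of its three terms is an empty category, and the recorded level between the other two is missing. Taken literally, it treats an event judged unlikely to be related as related, and an event judged possibly related as not related. No cut-point on the ordered four-level scale produces that set.

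Tolerability and safety are a secondary objective. The related-event counts by treatment group are one of the summaries a reader will use to judge tolerability of the two RPL554 doses against placebo. If the program follows the text, those counts omit every *Possibly* event. If the programmer silently corrects the text, the reported set differs from the one pre-specified. The SAP should settle this while the study is still blinded.

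**Working it through.** The SAP gives no figure to reproduce, so the check compares the recorded levels with the rule and then works out the effect on the counts.

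**1. Recorded levels against the rule**

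| Level | Recorded (SAP 4.5.1, protocol 8.2.3) | Related under SAP 6.4.7.1, literal | Related if *Probably* is a slip for *Possibly* |
|---|---|---|---|
| Not related | yes | no | no |
| Unlikely | yes | yes | yes |
| Possibly | yes | no | yes |
| Probably | no | yes (empty) | n/a |
| Definitely | yes | yes | yes |

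The literal rule captures 2 of the 4 recorded levels and the slip reading 3 of 4. The slip reading is the more plausible, because *Possibly* is the only recorded level between the other two named. The SAP does not say so.

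**2. Effect on the counts**

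Let U, P and D be the numbers of events rated Unlikely, Possibly and Definitely.

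- Literal count = U + D
- Slip-reading count = U + P + D
- Difference = P
- Share of the slip-reading count that is lost = P/(U + P + D)

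The number of patients with at least one related event falls by between 0 and P, because a patient with a *Possibly* event may also have an *Unlikely* or *Definitely* one.

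The documents give no expected event numbers. Purely as an illustration, assume U + P = 10 and D = 0:

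| U | P | Literal | Slip reading | Share lost |
|---|---|---|---|---|
| 10 | 0 | 10 | 10 | 0/10 = 0% |
| 8 | 2 | 8 | 10 | 2/10 = 20% |
| 5 | 5 | 5 | 10 | 5/10 = 50% |
| 2 | 8 | 2 | 10 | 8/10 = 80% |

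**3. How far *Definitely* can make up for the missing level**

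Protocol 8.2.3 requires all four criteria for *Definitely*. The third includes recurrence on re-exposure, and the attached note insists on an observed recurrence. Under protocol 5.1, "Patients will receive the following three single doses in a randomised sequence at Visit 2 to Visit 4", so each patient receives each treatment once. On the wording of the third criterion, an event seen at one visit only cannot be rated *Definitely* within the study, and *Possibly* is the only level above *Unlikely* open to it. The literal rule leaves out every event rated that way.

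Planned dosings are 10 completers × 3 visits = 30. Of these, 10 are at Visit 2, before any re-exposure in the study, so an event there cannot be *Definitely* when first assessed.

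**4. Outputs affected**

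SAP 8.1 plans six adverse event tables: 14.3.1.1 to 14.3.1.5 (five) and 14.3.2.1 (one). The rule enters two of them: one row of the overview (taken to be 14.3.1.1) and all of 14.3.1.3. The remaining rows of the overview and the other four tables do not use it.

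**The case against.** The strongest reply is that this is a one-word slip with little reach. SAP 4.5.1 gives the right levels, *Probably* matches no value in the data, and SAP 6.1 plans validation in a second package, so someone is likely to notice and query it. The primary objective is pharmacokinetic, about 10 patients complete, and no test or decision uses the related set. Every event still appears in "16.2.7.1 Listing of adverse events". All of that is fair and limits the consequence. It does not make the rule usable: validation against the same sentence can reproduce the error, and a listing does not correct a wrong summary count.

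A second reply concerns *Definitely*. The note in protocol 8.2.3 says re-exposure of the patient is not to be read as required, and protocol 8.2.2 recognises intermittent events with several episodes, so a recurrence might be seen without a second dose. The note does sit awkwardly beside the third criterion. That criterion names re-exposure and all the criteria must be met, so the stricter reading is supported, but how rare *Definitely* will be remains an inference. The main finding does not depend on it.

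Third, counting *Unlikely* as related may be deliberate. Protocol 8.2.3 itself describes *Possibly* as a link that looks unlikely but cannot be excluded, so treating everything except *Not related* as related is a coherent, cautious choice. That is right. The SAP gives no reason either way, so this part is a request for confirmation and not an error.

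**Conclusion.** The concern holds. As written, SAP 6.4.7.1 gives a wrong set: it counts *Unlikely* and *Definitely* events, omits *Possibly* events, and includes a level that cannot occur. The count of related events is short by exactly P compared with the slip reading, and the two readings agree only when no event is rated *Possibly*. That result needs no assumption. The 0% to 80% range does rest on assumed event numbers and shows only how the share lost varies.

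The effect is confined to two descriptive outputs, the causally related overview row and Table 14.3.1.3. SAE reporting, the listings, the remaining adverse event tables, and the PK and FEV₁ analyses are untouched. The rule should be corrected before lock, but it does not threaten the primary objective.

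**What to change.** Before database lock and unblinding, restate the related set in SAP 6.4.7.1 using recorded levels only. At minimum, replace *Probably* with *Possibly*, so that the set is Unlikely, Possibly or Definitely. In the same edit, have the sponsor confirm whether *Unlikely* is intended to count as related; if it is not, the set becomes Possibly or Definitely. State that the definition applies to the causally related row of the adverse event overview (Table 14.3.1.1, if that is the overview) and to Table 14.3.1.3.

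The cost is one SAP sentence and one line of programming. The four-level ratings are already collected, so no new data or CRF change is needed.

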6.4.7.2 Laboratory tests

Safety laboratory test data will be summarised by treatment group and time point. For continuous variables, the change from baseline (pre-dose at each treatment

visit) to each post-dose time point will also be calculated and summarised. Data will further be illustrated by shift tables (showing changes from low/normal/high) and shift plots for change over the study.

The baseline value will be defined as the last scheduled, unscheduled or repeat value collected prior to first dosing. The tabulation will only include scheduled visits; all unscheduled assessments will be displayed in the listing as appropriate.

All laboratory values will be listed showing reference ranges and flagging all abnormal findings and their clinical significance (CS or NCS). Out of reference range values will be flagged as high (H) or low (L). A similar listing including all post-dose laboratory values found abnormal, including the baseline result and clinical significance, will also be produced.

6.4.7.3 Vital Signs

Vital signs data will be summarised by treatment group and time point. The change from baseline (pre-dose at each treatment visit) to each post-dose time point will also be calculated and summarised. Data will further be illustrated by shift tables (showing changes from low/normal/high) and shift plots for the change from baseline to worst case during the treatment period.

The baseline value will be defined as the last scheduled, unscheduled or repeat value collected prior to dosing in a period. The tabulation will only include scheduled visits; all unscheduled assessments will be displayed in the listing as appropriate.

Vital signs will be listed showing reference ranges and flagging all abnormal findings and their clinical significance (CS or NCS). Out of reference range values will be flagged as high (H) or low (L). A similar listing including all post-dose vital signs values found abnormal, including the baseline result and clinical significance, will also be produced.

Further, for data collected during treatment days, graphics will include individual and mean value curves over time for each variable expressed as change from baseline.

6.4.7.4 12-Lead ECG

12-lead ECG data will be summarised and illustrated in the same way as vital signs data. In addition, for QTcF, a plot showing the baseline value of the treatment day on the x-axis versus the post-dose value indicating the largest absolute change on the y-axis will be constructed. QTcF data will also be summarised according to frequencies of values >450 ms, >480 ms and >500 ms and according to frequencies of shifts from baseline of the treatment day to post-dose of >30 ms and >60 ms.

6.4.7.5 Physical Examination

Physical examination data (changes in status between Visit 1 and Visit 5) will be listed.

6.4.7.6 Rescue Medication

Rescue medication used during the treatment visits will be summarised by treatment group and all individual use listed.

6.4.7.7 Concomitant Medications

Prior medications are defined as those with a stop date prior to the date of the first dose of study treatment. Concomitant medications are defined as those medications with either a start date or a stop date that is after the date of first dose of study

treatment. If the start date is unknown then it will be assumed to be concomitant unless the partial start date, or other data (i.e. stop date) indicates differently.

All prior and concomitant medications will be listed by reported name, medication class, standardised medication name, indication, dose, dose unit, route of administration, dosing frequency, start and end dates.

6.4.7.8 Pregnancy tests

Pregnancy test results, or reasons for not performing the test(s), from females at screening, pre-dose at each treatment visit and at end-of-study will be listed.

6.5 Determination of Sample Size

This is a sample size of convenience. No calculation of power was performed.

6.6 Statistical Issues

All hypothesis testing will be done using two-sided alternative hypotheses. P-values less than 5% will be considered statistically significant.

No adjustment for multiple testing will be done. A closed testing procedure will be applied: first the higher dose of RPL544 will be tested versus placebo and then, if statistically significant, the lower dose of RPL554 versus placebo. Finally the two doses of RPL554 will be compared.

Patients withdrawn after only one treatment period will not be included in the efficacy analyses. No imputation of missing data other than described under Section 6.4 will be performed.

Sensitivity analyses of pharmacodynamic data will be done to explore the impact of outliers or, for FEV₁ parameters, the use of rescue medication during the clinic visits.

All available data from all patients who have received study treatment will be listed and summarised. Any unscheduled or unplanned readings will be presented within the patient listings, but only the scheduled readings will be used in any summaries. If a visit is rescheduled due to variability in FEV₁ or other reason, the rescheduled visit will be listed and summarised as the valid visit.

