4.3 Removal of Patients from Therapy or Assessment

Investigators have the authority to ask for the withdrawal of a patient at any time for medical or non-compliance reasons. Should the Investigator decide it is necessary to withdraw any patient for specific reasons, this should be recorded in writing and discussed with the patient in question. Such reasons for withdrawal are expected to be medical or related to lack of co-operation by the patient.

If a patient withdraws following randomisation, every attempt should be made to contact the patient to determine the reason for withdrawal and to complete the recording of any available pharmacodynamic data and all adverse event data. If a patient agreed to enter the study and signed a consent form but withdrew from the study, or was withdrawn from the study, without receiving any study treatment, no further follow-up is necessary.

End of study visits will occur 3 to 10 days after the last dose of study treatment. All withdrawn patients will follow this routine unless it is considered by the Investigator that they require greater medical supervision and/or investigations and in which case an unscheduled visit prior to and in addition to the scheduled follow up visit may be performed.

If a patient decides to withdraw voluntarily, or is withdrawn by the Investigator responsible at any time, the reasons for withdrawal and results of all relevant tests will be recorded in the case report form (CRF). Patients who withdraw may be replaced.

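### The scheduled-readings-only rule reaches the QTcF threshold counts, worst-case displays and abnormal-findings tables, so these outputs can understate the most extreme ECG or vital sign observed

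*SAP*

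**What the plan says.** The general rule is in SAP 6.6: "Any unscheduled or unplanned readings will be presented within the patient listings, but only the scheduled readings will be used in any summaries". Protocol 10.4.8 has the same sentence, so the two documents agree.

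SAP 6.4.7.3 restates it for vital signs: "The tabulation will only include scheduled visits; all unscheduled assessments will be displayed in the listing as appropriate". SAP 6.4.7.2 does the same for laboratory tests. ECG inherits the vital-sign handling through SAP 6.4.7.4: "12-lead ECG data will be summarised and illustrated in the same way as vital signs data".

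The same sections plan outputs whose purpose is to find extremes. SAP 6.4.7.3 asks for "shift plots for the change from baseline to worst case during the treatment period". SAP 6.4.7.4 states that "QTcF data will also be summarised according to frequencies of values >450 ms, >480 ms and >500 ms", adds counts of shifts above 30 and 60 ms, and plots baseline QTcF against the post-dose value with the largest absolute change. SAP 8.1 lists Table "14.3.5.2 Summary of abnormal findings on vital signs", with counterparts for ECG (14.3.5.4) and laboratory data (14.3.4.3).

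Unscheduled values are expressly allowed into one derived quantity, the pre-dose baseline: "The baseline value will be defined as the last scheduled, unscheduled or repeat value collected prior to dosing in a period".

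**The concern.** A mean at 2 hours should use the 2-hour readings, and a scheduled-only rule protects it. A threshold count or worst case asks a different question: did this patient, on this treatment, ever reach that value? A reading taken off schedule because a patient has symptoms, or to follow up an odd result, is among those most likely to be extreme. The rule sends it to a listing and leaves it out of the count.

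Safety and tolerability are a secondary objective, and protocol 1.2 names hypotension and tachycardia as potential risks from non-clinical data. A reader who relies on the tables could see no patient above a limit when the database contains one, and a display labelled worst case might not show the worst case.

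**Working it through.** The plan gives no figure to reproduce: SAP 6.5 states that the sample size is one of convenience, without a power calculation. The check is a reading of the rules against each output, plus a count.

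**Does any text exempt the extreme-value outputs?**

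| Output | How the SAP describes it | Reach of the rule |
|---|---|---|
| QTcF counts above 450/480/500 ms; shifts above 30/60 ms (6.4.7.4) | summarised by frequency | Direct: it is a summary |
| Tables 14.3.5.2, 14.3.5.4 and 14.3.4.3 (8.1) | titled as summaries | Direct |
| Worst-case shift plots (6.4.7.3, carried to ECG by 6.4.7.4) | a plot | By the breadth of SAP 6.6; no exemption |
| QTcF largest-change plot (6.4.7.4) | a plot | As above |

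No exemption appears in either document. Visits rescheduled for FEV₁ variability or another reason do count as valid visits, so they are not affected.

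**Are post-dose repeats excluded?** SAP 6.6 does not name them. Their exclusion is inferred from its limit to scheduled readings, and from the baseline rule, which treats scheduled, unscheduled and repeat values as three kinds.

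**Can off-schedule readings arise?** Yes. Protocol 6 permits repeat and unscheduled procedures at the Investigator's discretion. Scheduled post-dose times (SAP 4.5.3 and 4.5.5) leave gaps:

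- ECG at 1, 2, 4 and 8 h: 4 × 3 visits = 12 per patient; 4 × 10 completers = 40 per treatment. Nothing is scheduled before 1 h or between 4 h and 8 h.
- Vital signs at 0.5, 1, 2, 4, 6 and 8 h: 6 × 3 = 18 per patient; 6 × 10 = 60 per treatment.
- Neither is scheduled after 8 h.

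**Size of one omission.** With 10 patients on a treatment (10 completers, SAP 3.3), one patient is 1/10 = 10 percentage points. Non-completers are replaced and the safety set keeps anyone with post-dose safety data from one visit, so the denominator may be slightly larger; at an assumed 12 it would be 1/12 = 8.3 points.

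As an illustration, suppose one patient crosses a QTcF limit only on an off-schedule ECG:

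- Observed 1/10. Exact 95% limits: lower 1 − 0.975^(1/10) = 0.3%; upper 44.5%, which solves (1 − p)^10 + 10p(1 − p)^9 = 0.025.
- Tabulated 0/10. Exact 95% limits: 0% to 1 − 0.025^(1/10) = 30.8%.

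The intervals overlap heavily, and the SAP plans none for safety data. What changes is whether the table shows a case at all.

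**The case against.** The strongest reply is that nothing is hidden. SAP 6.4.7.2 and 6.4.7.3 require a listing of all abnormal post-dose values with baseline and clinical significance, and ECG follows suit. With about 10 patients per treatment it can be read line by line. This stands as mitigation, and it rules out any suggestion of concealment. It does not make the threshold count right.

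Several stronger readings are tempting, and the documents do not support them:

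- *That every safety summary is affected, or that an unwell patient disappears from the tables.* The rule concerns readings. Adverse events (SAP 6.4.7.1) and rescue medication (SAP 6.4.7.6) are summarised separately. Palpitations that prompt an extra ECG would be counted as an adverse event.
- *That the rule discards the data from the extra visit for withdrawn patients.* Protocol 4.3 foresees cases where "they require greater medical supervision and/or investigations and in which case an unscheduled visit prior to and in addition to the scheduled follow up visit" is possible, but names no ECG or vital signs there.
- *That readings after 8 h are lost through this rule alone.* The declared ECG and vital-sign endpoint runs over 8 hours (SAP 4.1.2), so later readings fall outside it in any case.
- *That allowing unscheduled baselines but not unscheduled post-dose values is a bias.* A last pre-dose value and a post-dose extreme are different quantities, and the difference by itself shows no bias.
- *That a QT problem is expected.* Protocol 1.2 names hypotension and tachycardia, not QT prolongation, and entry requires QTcF of at most 450 ms.

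There is also room for a softer reading. The vital-sign text restricts tabulation to scheduled visits, so an extra ECG within a treatment visit might be thought admissible, and SAP 6.6 also says that all available data from dosed patients will be summarised as well as listed. But the sentence that follows is specific and covers all summaries. It governs unless the text is changed.

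Finally, discretionary readings give some patients more chances to cross a limit, and staff supervising dosing are unblinded (protocol 5.8). That cost is real; a footnote discloses it but does not remove it.

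**Conclusion.** The point holds for summaries of readings. As written, SAP 6.6 and protocol 10.4.8 exclude off-schedule post-dose ECGs and vital signs from the QTcF threshold and shift counts and from Tables 14.3.5.2 and 14.3.5.4. On the literal reading they also exclude them from the worst-case and largest-change plots. These outputs could then understate the observed extreme, while the listings and adverse event tables remain complete.

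The size is 10 percentage points per omitted patient at 10 per treatment. That assumes an off-schedule reading that crosses a limit no scheduled reading crosses; the documents give no rate for this, so no expected effect can be stated. The change is a cheap improvement, not a threat to the primary pharmacokinetic objective.

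**What to change.** 1. In SAP 6.6, 6.4.7.2 and 6.4.7.3, limit the scheduled-only rule to descriptive statistics by time point.
2. In SAP 6.4.7.3 and 6.4.7.4, state that the ECG and vital-sign threshold, shift, worst-case and abnormal-findings outputs (including Tables 14.3.5.2 and 14.3.5.4) use all post-dose readings in the treatment period, whether scheduled, unscheduled or repeat, assigned to the treatment given in that period. Say where the period ends, given the 8-hour endpoint, and how a repeat taken because the first tracing was technically faulty is handled.
3. Footnote any count that rests only on unscheduled readings.
4. For laboratory Table 14.3.4.3, include unscheduled post-dose values as a summary over the whole study, without attributing them to one treatment. Laboratory tests are scheduled only at Visits 1 and 5, so assigning values to the last treatment would credit every Visit 5 abnormality to whichever treatment came third.
5. Amend protocol 10.4.8 to match, or record the change in SAP 6.8.

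The cost is a few sentences and limited programming on readings already collected and listed. The downside is the unequal chance of crossing a limit, which the footnote makes visible.
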